3.10. Missing, Unused, and Spurious Data

In general, there will be no substitutions made to accommodate missing data points. All data recorded on the case report form (CRF) will be included in data listings that will accompany the CSR. Data collected at multiple time points throughout the study will be presented in chronological order in the data listings according to assessment date/time.

Handling of partial dates for determining whether an AE is treatment-emergent is discussed in [Section 4.5.2](#). Handling of partial dates for determining concomitant medication is discussed in [Section 4.5.6](#).

3.11. Visit Windows

It is expected that all visits will occur according to the protocol schedule of assessments. All data will be tabulated per the evaluation visit as recorded on the CRF even if the assessment is outside of the window for that study visit. In data listings, the study day relative to Day 0 (day of first dose) will be presented.

Unscheduled visits will be included in data listings, but no assignment to a study visit will be made for the purpose of summary tabulations.

3.12. Interim Analyses

No interim analyses are planned for this study.

4. STUDY ANALYSES

4.1. Subject Disposition

Subject disposition will be tabulated and include the number enrolled, the number dosed, the number in each subject population for analysis, the number who completed the study (as indicated on the Study Completion CRF), the number who withdrew prior to completing the study and reason(s) for withdrawal. Summary data will be presented by dose group and overall.

A by-subject data listing of study completion information including the reason for premature study withdrawal, if applicable, will be presented.

4.2. Demographics and Baseline Characteristics

Demographics and baseline characteristics will be summarized and presented by dose group and overall for the ITT population.

Age, height, weight, and BMI will be summarized using descriptive statistics (number of subjects, mean, SD, median, minimum, and maximum). Sex, race, ethnicity, and country will be summarized by presenting the numbers and percentages of subjects in each category.

Baseline disease characteristics will be summarized by presenting the numbers and percentages of subjects with or without the V30M mutation and with or without prior exposure to TTR02. Concurrent use of TTR stabilizer (Tafamidis or Diflunisal) will also be summarized.

All demographic and baseline data will be provided in data listings.

Medical history and prior surgeries will be presented in a data listing. Pregnancy and virology test results will be presented in data listings.

4.3. Pharmacodynamic Evaluation

4.3.1. Total Serum TTR (ELISA)

Serial measurements and changes from baseline of serum TTR through Day 208 will be summarized for each scheduled time point using descriptive statistics. Percent change from baseline will also be summarized. Ninety-five percent CIs for percent change will be presented. An overall summary of percent reduction in TTR will include the maximum percent reduction per dose group, dose group means (SD) at individual and group nadirs (defined below), and dose group means (SD) at Day 28 and Day 56 (Day 21 and Day 42 for optional cohorts dosed every 3 weeks).

The individual nadir TTR value, defined as the lowest observed TTR value from Day 1 to the Day 28 premedication assessment (Day 21 for optional cohorts dosed every 3 weeks), will be

determined for each subject. The nadir value will be plotted for each subject, grouped by dose group. Dose group means will be indicated on the plot. The value of the percent reduction associated with the nadir will be plotted similarly. The nadir value from the Day 29 to Day 56 interval (Day 22 to Day 42 for optional cohorts dosed every 3 weeks) will also be determined and plotted.

The group nadir TTR value, defined as the lowest observed mean percent TTR reduction from baseline from Day 1 to the Day 28 premedication assessment (Day 21 for optional cohorts dosed every 3 weeks), will be determined for each dose/regimen group. The group nadir value will be plotted for each group, along with standard error bars. The group nadir value from the Day 29 to Day 56 interval (Day 22 to Day 42 for optional cohorts dosed every 3 weeks) will also be determined and plotted.

The area under the concentration-time curve (AUC) will be calculated for serum TTR. The AUC will be calculated using the daily TTR concentrations starting from baseline, defined as the average of all pre-dose values, and continuing to the Day 28 premedication assessment (Day 21 for optional cohorts dosed every 3 weeks). The trapezoidal rule will be used for the calculation of AUC. For the purpose of this AUC calculation, it is assumed that the collection times are in multiples of equal 24 hour intervals. For example, the interval from Day 2 to Day 4 will be 48 hours, irrespective of actual assessment times. AUC will be summarized using descriptive statistics. A similar calculation and summary will be performed for the AUC calculated from Day 28 to Day 56 (Day 21 to Day 42 for optional cohorts dosed every 3 weeks).

TTR levels over time will be plotted. Each subject's TTR levels will be joined by a line, and each subject within a dose group will have a different symbol. A separate plot will be produced for each dose group. In addition, the average of each dose group (with standard error bars) will be plotted versus time. Dose group means (with standard error bars) for percent change from baseline will be plotted over time.

The pharmacodynamics assessment for use in the PK/PD analysis will be similar to that described above, but may include additional PD analyses which will be used for the purpose of PK/PD analysis. The methods for the PK/PD analysis will be described in the PK and PK/PD analysis plans and the analysis result will be reported in the separate PK and PK/PD report which will be appended to the CSR.

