### 7.4 Pharmacokinetic Evaluations

### 7.4.1 Plasma Pharmacokinetics

The PK parameter estimates and dose proportionality profiles of ALN-TTR02 will be determined for ALN-TTR02 siRNA (ALN-18328) and liposome lipid components, DLin-MC3-DMA and PEG2000-C-DMG. The plasma concentration-time profiles for ALN-18328, DLin-MC3-DMA, and PEG2000-C-DMG will be determined and used in the PK analysis for all dose cohorts. In addition, free and encapsulated concentrations of siRNA will be determined in plasma at specified time points (see Table 1-1) for cohort 3 and onward, including any optional cohorts. The drug concentrations in the lower cohorts are expected to be undetectable for this analysis.

Blood sample collection times are included in the schedule of events (see Table 1-1). Plasma PK samples (siRNA and lipids) will be collected pre-dose (within 1 hour of planned dosing start), at EOI, and then 5, 10, and 30 minutes, and at 1, 2, 4, 6, 24, and 48 hours post infusion. Samples will also be collected on Days 7, 14, 21, 35, 42, 49, 56, 112, and 208 post infusion as well as at the ET visit (if applicable); for optional cohorts

dosed once every 3 weeks, samples will be collected on Days 7, 14, 21, 28, 35, 42, 56, 112, and 208 post infusion as well as at the ET visit (if applicable).

For the PK blood draws, the sampling windows are  $\pm 1$  minute for the 5- and 10- minute draws;  $\pm 2$  minutes for the 30-minute draws;  $\pm 5$  minutes for the 1-, 2-, 4-, and 6-hour draws; and  $\pm 120$  minutes for the 24- and 48-hour draws.

The EOI will usually occur at 60 minutes after the start of infusion, except in patients where the infusion has been prolonged. If the infusion is stopped, a PK blood sample will be taken when the infusion is stopped, and this sample will be treated as the EOI sample if the infusion is restarted. All remaining PK samples will be collected according to the schedule of assessments when the dose is completed (i.e., all post-infusion times are relative to the EOI, regardless of the duration of infusion).

In the event that a patient receives only 1 dose of study drug, plasma PK samples should be collected pre-dose (within 1 hour of planned dosing start), EOI, and then 5, 10, and 30 minutes; and 1, 2, 4, 6, 24 and 48 hours post infusion; and at Day 208.

Details of sample collection and processing for PK analyses will be included in a laboratory manual.

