2. SUBJECT POPULATION

2.1. Population Definitions

The following patient populations (i.e., analysis sets) may be evaluated and used for presentation of the data:

- Intent-to-Treat (ITT) Analysis Set: All patients who were enrolled and received study treatment.
- Per-Protocol (PP) Analysis Set: All patients in the ITT analysis set who had no major protocol violations.
- Pharmacokinetic (PK) Analysis Set: All patients in the ITT analysis set who have adequate data to determine a full PK profile.

The ITT analysis set is the primary population for the analysis of PD and safety parameters. A secondary analysis of PD parameters will be performed for the PP analysis set. The PK analysis set is the primary population for the analysis of PK parameters.

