7. CLINICAL STUDY REPORT APPENDICES

7.1. Statistical Tables to be Generated

Table 14.1.1	Subject Enrollment and Disposition, Overall and by Dose Group
Table 14.1.2	Demographic and Baseline Characteristics (Intent-to-Treat Analysis Set)
Table 14.1.3	Baseline Disease Characteristics (Intent-to-Treat Analysis Set)
Table 14.2.1.1A	Summary of Serial TTR [ELISA] (ug/mL) Measurements by Time Point – Q4W Cohorts (Intent-to-Treat Analysis Set)
Table 14.2.1.1B	Summary of Serial TTR [ELISA] (ug/mL) Measurements by Time Point – Q3W Cohorts (Intent-to-Treat Analysis Set)
Table 14.2.1.2A	Summary of Serial Vitamin A (umol/L) Measurements by Time Point - Q4W Cohorts (Intent-to-Treat Analysis Set)
Table 14.2.1.2B	Summary of Serial Vitamin A (umol/L) Measurements by Time Point - Q3W Cohorts (Intent-to-Treat Analysis Set)
Table 14.2.1.3A	Summary of Serial Retinol Binding Protein (umol/L) Measurements by Time Point – Q4W Cohorts (Intent-to-Treat Analysis Set)
Table 14.2.1.3B	Summary of Serial Retinol Binding Protein (umol/L) Measurements by Time Point – Q3W Cohorts (Intent-to-Treat Analysis Set)
Table 14.2.2.1A	Summary of Serial TTR [ELISA] (ug/mL) Measurements by Genotype – Q4W Cohorts (Intent-to-Treat Analysis Set)
Table 14.2.2.1B	Summary of Serial TTR [ELISA] (ug/mL) Measurements by Genotype – Q3W Cohorts (Intent-to-Treat Analysis Set)
Table 14.2.2.2A	Summary of Serial TTR [ELISA] (ug/mL) Measurements by Mutation – Q4W Cohorts (Intent-to-Treat Analysis Set)
Table 14.2.2.2B	Summary of Serial TTR [ELISA] (ug/mL) Measurements by Mutation – Q3W Cohorts (Intent-to-Treat Analysis Set)
Table 14.2.2.3A	Summary of Serial TTR [ELISA] (ug/mL) Measurements by TTR Stabilizer Use – Q4W Cohorts (Intent-to-Treat Analysis Set)
Table 14.2.2.3B	Summary of Serial TTR [ELISA] (ug/mL) Measurements by TTR Stabilizer Use – Q3W Cohorts (Intent-to-Treat Analysis Set)
Table 14.2.3.1A	Summary of Percent Reduction in Serum TTR (ELISA) by Dose Group – Q4W Cohorts (Intent-to-Treat Analysis Set)
Table 14.2.3.1B	Summary of Percent Reduction in Serum TTR (ELISA) by Dose Group – Q3W Cohorts (Intent-to-Treat Analysis Set)
Table 14.2.3.2A	Summary of Percent Reduction in Serum Wild Type TTR (LCMS/MS) by Dose Group – Q4W Cohorts (Intent-to-Treat Analysis Set – V30M Subjects)
Table 14.2.3.2B	Summary of Percent Reduction in Serum Wild Type TTR (LCMS/MS) by Dose Group – Q3W Cohorts (Intent-to-Treat Analysis Set – V30M Subjects)

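### The TTR summaries for the second dosing interval set no condition that dose 2 was given, so one-dose patients can be averaged in and can shift a small group mean in either direction

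*SAP*

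**What the plan says.** **Analysis set.** SAP 2.1 defines ITT as "All patients who were enrolled and received study treatment". It then states: "The ITT analysis set is the primary population for the analysis of PD and safety parameters". It also promises that "A secondary analysis of PD parameters will be performed for the PP analysis set"; the PP set removes only patients with major protocol violations.

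**Second-interval measures.** SAP 4.3.1 asks for "The nadir value from the Day 29 to Day 56 interval" (Day 22 to Day 42 in 3-week cohorts), both per patient and as a group nadir. For the area under the TTR curve: "A similar calculation and summary will be performed for the AUC calculated from Day 28 to Day 56" (Day 21 to Day 42). The overall summary of percent reduction includes "dose group means (SD) at Day 28 and Day 56" (Day 21 and Day 42). None of these depends on receipt of dose 2. SAP 4.3.2 uses the same nadir definitions for vitamin A and RBP.

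**Planned tables.** Every PD table in SAP 7.1, including "Summary of Percent Reduction in Serum TTR (ELISA) by Dose Group", is for the ITT set or its V30M subset. No PP version is listed.

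**Early termination and missing data.** SAP 3.9 puts data from an early-termination visit before Day 56 into the Day 56 summary. SAP 3.10 makes no general substitution for missing values.

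**One-dose patients.** Protocol 3.1 and 5.7.1 withhold dose 2 after a stated transaminase finding. Protocol 5.6 rechecks eligibility before dose 2. Protocol 5.7.4 halts dosing after a DLT pending committee review. Protocol 7.4.1 has a plasma sampling rule that begins: "In the event that a patient receives only 1 dose of study drug".

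**The concern.** The second-interval measures will naturally be read as the response after dose 2, yet a patient qualifies for them by calendar day and one infusion. Protocol 1.3 reports that TTR lowering after a single dose was reversible. In a patient who missed dose 2, the lowest value in the Day 29-56 window would therefore tend to be the first one sampled, a remnant of dose 1.

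The laboratory shift tables in SAP 4.5.3 are tied to values after each dose. The PD measures have no such tie.

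What is at stake is how the repeat-dose PD results are described in groups of a few patients. PD on total serum TTR is a secondary objective, the study gives two consecutive doses, and the protocol expects the recommended Phase 3 dose and regimen to be derived from it. Several routes to a missed second dose are safety-related, so such patients need not be spread evenly over dose groups.

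**Working it through.** **1. The plan's own count.** SAP 3.1: 4 dose levels x 3 + 5 optional cohorts x 3 = 27, as stated. It gives no effect size, SD or power for TTR, and no expected number of one-dose patients. All response values below are assumptions.

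**2. Who enters a second-interval mean.**
- A one-dose patient sampled after Day 28 is in ITT and contributes to the nadir, AUC and by-visit rows.
- A one-dose patient with no sample after Day 28 contributes nothing to the nadir or AUC (SAP 3.10).
- A 4-week patient who leaves before dose 2 with an early-termination sample contributes that value to the Day 56 row (SAP 3.9). In 3-week cohorts the rule reaches the Day 56 row but not the Day 42 landmark.

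**3. Size of the shift.** Let n be the patients with data, k those among them without dose 2, R2 the mean reduction in two-dose patients and R1 that in one-dose patients.

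Shift = restricted mean - ITT mean = (k/n) x (R2 - R1)

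For k = 1, in percentage points:

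| Assumed gap R2 - R1 | n=3 | n=4 | n=6 | n=9 |
|---|---|---|---|---|
| 10 | 3.3 | 2.5 | 1.7 | 1.1 |
| 30 | 10.0 | 7.5 | 5.0 | 3.3 |
| 50 | 16.7 | 12.5 | 8.3 | 5.6 |
| 70 | 23.3 | 17.5 | 11.7 | 7.8 |

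n=3 is a single cohort; n=4 is a cohort with one replacement (Protocol 4.5.3), since the replaced patient stays in ITT; n=6 and n=9 are cohorts pooled under SAP 3.5. The same k/n factor applies to mean AUC, with the gap in AUC units.

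**4. Example, ITT too low.** Two patients at 80% and one undosed at 20%: (80 + 80 + 20)/3 = 60.0%, SD 34.6. With the undosed patient at 40%: 66.7%, SD 23.1. The restricted mean is 80% in both cases, and the SD comes wholly from mixing.

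**5. Example, ITT too high.** A patient leaves near the dose-1 nadir at an assumed 85%, and that value is counted as Day 56. If two dosed patients have recovered to 50, 60 or 70% by Day 56, the ITT mean is 61.7, 68.3 or 75.0%. For the middle case, (60 + 60 + 85)/3 = 68.3. The reduction is overstated by 11.7, 8.3 or 5.0 points.

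**6. Chance of at least one one-dose patient.** 1 - (1 - p)^m for an assumed independent rate p:

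| p | group of 3 | all 27 |
|---|---|---|
| 2% | 5.9% | 42% |
| 5% | 14.3% | 75% |
| 10% | 27.1% | 94% |
| 20% | 48.8% | 99.8% |

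Independence is itself doubtful, because a halt after a DLT could cost several patients dose 2 together.

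**7. Precision cost of restricting.** 95% CI half-width = t(0.975, n-1) x SD/sqrt(n). This is 2.48 SD at n=3 and 8.98 SD at n=2.

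**The case against.** The strongest reply is that ITT by assigned cohort is a legitimate description of what happens to patients allocated to a regimen, and that restricting to dose-2 recipients selects on a post-treatment event that may be linked to tolerability. That stands. It could flatter a poorly tolerated dose, and it is the reason not to replace the ITT summaries.

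The plan also has mitigations. Individual profiles and nadirs are plotted, dosing and PD are listed by subject, and nothing is formally tested. A one-dose patient could thus be found, and no formal conclusion rests on these means. The group means, SDs, CIs and AUCs would still include that patient, and no PD output is specified to flag one. The PP analysis is not a reliable remedy: withholding dose 2 under the protocol's own rule is compliance, not a violation, and no PP table is listed.

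Follow-up is the main uncertainty. Protocol 4.5.2 has patients withdrawn for an adverse event followed as scheduled, but other withdrawals lead to an early-termination visit. The one-dose rule in Protocol 7.4.1 covers plasma PK only, with samples to 48 hours and then Day 208. TTR sampling in the second window is therefore possible for one-dose patients but not assured.

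A reader might go further in ways the documents do not support:
- *That the repeat-dose effect is diluted.* No one-dose patient is known to exist, and step 5 shows that the Day 56 bias can run the other way.
- *That the groups always have 3 patients.* Pooling and replacement can enlarge them.
- *That the secondary objective is the effect of the two-dose regimen.* It is preliminary evidence of the PD effect of ALN-TTR02; multiple doses appear in the primary, safety objective.
- *That less tolerated doses must be hit hardest, or that the Phase 3 choice is compromised.* The first is plausible but undocumented. The second cannot be judged, because the PK/PD analysis is in a separate plan.

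**Conclusion.** The concern holds as a gap in the analysis rule. The second-interval PD summaries can include patients who never received dose 2, and the Day 56 row can include values taken before dose 2 was due. One such patient shifts the group mean by the gap divided by n: for an assumed 50-point gap, from 16.7 points at n=3 to 5.6 at n=9, with the sign depending on when the patient was sampled.

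This rests on an assumed gap, on at least one one-dose patient, and on that patient having a sample in the window or an early-termination value. The study is descriptive, so the consequence is a group summary that could be misattributed to dose 2, not a false test result. It is worth correcting because the data needed are already recorded.

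**What to change.** In SAP 4.3.1 and 4.3.2, for every PD summary after the dose-2 day (nadir Day 29-56, AUC Day 28-56, percent reduction at Day 56, by-visit rows from Day 29; for 3-week cohorts nadir Day 22-42, AUC Day 21-42, Day 42, and rows from Day 22):

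1. Add a summary restricted to ITT patients who received the second infusion. Show it with its n beside the ITT result, and use it when describing the effect after dose 2. State whether a partial second infusion counts; Protocol 5.8 already has an 80% completion threshold that could serve for this analysis definition.
2. Identify one-dose patients in a separate line or listing.
3. In SAP 3.9, exempt PD from the early-termination rule where the value was taken before dose 2, so that it does not enter a Day 56 PD row.
4. Keep the dose-1-interval summaries on all ITT patients.

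The cost is SAP wording, one filter on recorded dosing data and a few extra table rows. The restricted rows will have smaller n and wider intervals (8.98 SD at n=2 against 2.48 SD at n=3). They also select on receipt of dose 2, which is why the ITT result stays alongside.

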3.5. Methods of Pooling Data

Data will be summarized separately for each dose group (i.e., dose level and regimen). Data from expansion cohorts that are dosed at the same level and regimen as a previous cohort will be pooled with the previous cohort for presentation by dose group. In addition, safety data will be presented overall.

Data will be tabulated separately for dose groups dosed 4 weeks apart and dose groups dosed 3 weeks apart, if applicable.

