4.3.2. Vitamin A and Retinol Binding Protein

Observed values and changes from baseline in vitamin A through Day 208 will be summarized for each scheduled time point using descriptive statistics. Percent change from baseline will also be summarized. Ninety-five percent CIs for percent change will be presented.

Vitamin A levels over time will be plotted. Each subject's vitamin A levels will be joined by a line, and each subject within a dose group will have a different symbol. A separate plot will be produced for each dose group. In addition, the average of each dose group (with standard error bars) will be plotted versus time. Dose group means (with standard error bars) for percent change from baseline will be plotted over time. Percent reduction from baseline at individual and group nadirs will be plotted as described above for serum TTR.

The above summaries will also be performed for RBP.

A scatter plot of total serum TTR protein versus vitamin A and RBP, all normalized to their respective baseline values, will be produced. The plot will include Spearman's correlation coefficients (ρ) and the p-values from the tests of $\rho = \text{zero}$, to assess the strength of the correlations between serum TTR and vitamin A and between serum TTR and RBP.

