7.3. Figures to be Generated

Figure 14.2.1.1	Individual TTR (ELISA) Levels over Time
Figure 14.2.1.2	Individual Wild Type TTR (LCMS/MS) Levels over Time
Figure 14.2.1.3	Individual Mutant TTR (LCMS/MS) Levels over Time
Figure 14.2.2.1	Mean TTR (ELISA) Levels by Dose Group over Time
Figure 14.2.2.2	Mean Wild Type TTR (LCMS/MS) Levels by Dose Group over Time
Figure 14.2.2.3	Mean Mutant TTR (LCMS/MS) Levels by Dose Group over Time
Figure 14.2.3.1	Mean Percent Change from Baseline in TTR (ELISA) by Dose Group over Time
Figure 14.2.3.2	Mean Percent Change from Baseline in Wild Type TTR (LCMS/MS) by Dose Group over Time
Figure 14.2.3.3	Mean Percent Change from Baseline in Mutant TTR (LCMS/MS) by Dose Group over Time
Figure 14.2.4.1.1	TTR (ELISA) at Individual Nadir by Dose Group
Figure 14.2.4.1.2	Mean Percent Change from Baseline in TTR (ELISA) at Individual Nadir by Dose Group
Figure 14.2.4.2.1	Wild Type TTR (LCMS/MS) at Individual Nadir by Dose Group
Figure 14.2.4.2.2	Mean Percent Change from Baseline in Wild Type TTR (LCMS/MS) at Individual Nadir by Dose Group
Figure 14.2.4.3.1	Mutant TTR (LCMS/MS) at Individual Nadir by Dose Group
Figure 14.2.4.3.2	Mean Percent Change from Baseline in Mutant TTR (LCMS/MS) at Individual Nadir by Dose Group
Figure 14.2.5.1	Mean Percent Change from Baseline in TTR (ELISA) at Group Nadir by Dose Group
Figure 14.2.5.2	Mean Percent Change from Baseline in Wild Type TTR (LCMS/MS) at Group Nadir by Dose Group
Figure 14.2.5.3	Mean Percent Change from Baseline in Mutant TTR (LCMS/MS) at Group Nadir by Dose Group
Figure 14.2.6	Mean Percent Change from Baseline in TTR (ELISA) at Individual Nadir by Dose Group and Stabilizer Use – 300 µg/kg Subjects
Figure 14.2.7.1	Area under the TTR (ELISA) Concentration-Time Curve
Figure 14.2.7.2	Area under the Wild Type TTR (LCMS/MS) Concentration-Time Curve
Figure 14.2.7.3	Area under the Mutant TTR (LCMS/MS) Concentration-Time Curve
Figure 14.2.8	Individual Vitamin A Levels over Time
Figure 14.2.9	Mean Vitamin A Levels by Dose Group over Time

Figure 14.2.10	Mean Percent Change from Baseline in Vitamin A by Dose Group over Time
Figure 14.2.11	Mean Percent Change from Baseline in Vitamin A at Individual Nadir by Dose Group over Time
Figure 14.2.12	Mean Percent Change from Baseline in Vitamin A at Group Nadir by Dose Group over Time
Figure 14.2.13	Individual Relative Retinol Binding Protein Levels over Time
Figure 14.2.14	Mean Retinol Binding Protein Levels by Dose Group over Time

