Figure 14.2.15	Mean Percent Change from Baseline in Retinol Binding Protein by Dose Group over Time
Figure 14.2.16	Mean Percent Change from Baseline in Retinol Binding Protein at Individual Nadir by Dose Group over Time
Figure 14.2.17	Mean Percent Change from Baseline in Retinol Binding Protein at Group Nadir by Dose Group over Time
Figure 14.3.1	Individual Liver Function Tests over Time
Figure 14.3.2	Mean Liver Function Tests by Dose Group over Time
Figure 14.3.3	Individual Cytokines and CRP over Time
Figure 14.3.4	Mean Cytokines and CRP by Dose Group over Time
Figure 14.3.5	Individual Complement Factor (Bb) over Time
Figure 14.3.6	Mean Complement Factor (Bb) by Dose Group over Time
Figure 14.3.7	Maximum Fold Change from Baseline for CRP
Figure 14.3.8	Maximum Fold Change from Baseline for Complement Factor (Bb)
Figure 14.3.9	Maximum Fold Change from Baseline for Cytokines

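### SAP 4.3.1 defines the group TTR nadir as the lowest mean percent reduction, which on the ordinary scale is the least-suppressed visit (minor; wrong as written)

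*SAP*

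**What the plan says.** SAP 4.3.1 defines two nadirs for total serum TTR.

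- **Individual nadir:** "defined as the lowest observed TTR value from Day 1 to the Day 28 premedication assessment", with Day 21 as the end point for cohorts dosed every 3 weeks.
- **Group nadir:** "defined as the lowest observed mean percent TTR reduction from baseline", over the same window and for each dose and regimen group.

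Both are derived again after the second dose; for the group version the text reads "The group nadir value from the Day 29 to Day 56 interval" (Day 22 to Day 42 for cohorts dosed every 3 weeks).

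The same section says how the results are summarised: "An overall summary of percent reduction in TTR will include the maximum percent reduction per dose group", together with dose-group means and SDs at the individual and group nadirs. SAP 4.3.2 carries the rule to vitamin A: "Percent reduction from baseline at individual and group nadirs will be plotted as described above for serum TTR", and then extends its summaries to RBP.

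The figure list in SAP 7.3 uses the other scale. Figure 14.2.5.1 is "Mean Percent Change from Baseline in TTR (ELISA) at Group Nadir by Dose Group", and Figures 14.2.12 (vitamin A) and 14.2.17 (RBP) are titled in the same way.

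**The concern.** A nadir is a low point of the marker, and so a high point of the reduction. Asking for the lowest reduction reverses this. The sentence is a derivation rule, and no other part of the SAP defines the term. A programmer who followed it to the letter would report the visit at which the drug had done least and label it the nadir.

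TTR lowering is the pharmacodynamic secondary objective, and the group nadir is a named element of its percent-reduction summary. Under the literal rule, Figure 14.2.4.1.2 (individual nadir) and Figure 14.2.5.1 (group nadir) would show opposite extremes of the same data under the same word. The vitamin A and RBP plots would inherit the error.

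**Working it through.** **Direction (no data needed).** Let B be a patient's baseline and T the TTR value at a visit.

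- Percent reduction: R = 100 × (B − T) / B
- Percent change: C = 100 × (T − B) / B = −R

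The sign relation survives averaging, so at each visit the group mean of R is minus the group mean of C.

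- Individual nadir: with B fixed, the smallest T gives the largest R, which is the most suppression.
- Group nadir as written: the smallest mean R is the largest (least negative) mean C, which is the least suppression.
- Group nadir if *change* had been written: the smallest mean C is the largest mean R, which is the most suppression.

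Whenever a group's mean reduction varies between visits, the literal rule and a true nadir therefore select different visits.

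**Which scale the text uses.** SAP 4.3.1 names percent change separately from percent reduction, and takes the maximum reduction as the extreme of effect. Both point to reduction as a positive quantity. The figure titles in SAP 7.3 are on percent change, where *lowest* is the correct end. The simplest explanation is that the definition took its adjective from one scale and its noun from the other.

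**Illustration.** The plan states no figure to reproduce, and neither document gives a per-visit TTR profile for these patients. The group mean TTR values below, as % of baseline, are assumptions.

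| Assumed profile | D1 | D2 | D7 | D10 | D14 | D21 | D28 |
|---|---|---|---|---|---|---|---|
| Weak | 99 | 97 | 85 | 80 | 84 | 90 | 96 |
| Middle | 95 | 85 | 55 | 50 | 55 | 68 | 82 |
| Strong | 92 | 75 | 22 | 15 | 18 | 30 | 50 |

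With R = 100 − value:

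| Assumed profile | Literal rule (smallest R) | True nadir (largest R) | Lowest percent change |
|---|---|---|---|
| Weak | 100 − 99 = 1% (Day 1) | 100 − 80 = 20% (Day 10) | −20% (Day 10) |
| Middle | 100 − 95 = 5% (Day 1) | 100 − 50 = 50% (Day 10) | −50% (Day 10) |
| Strong | 100 − 92 = 8% (Day 1) | 100 − 15 = 85% (Day 10) | −85% (Day 10) |

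**Sensitivity to shape.** Take four other assumed shapes whose least-suppressed visit stands at 0% (slow onset, Day 1), 6% (central, Day 1), 10% (fast recovery, Day 28) and 20% (fast onset, Day 1) of the maximal effect. If the true nadir is 80%, the literal rule returns 0, 0.06 × 80 = 4.8, 0.10 × 80 = 8 and 0.20 × 80 = 16%. The corresponding ranges are 0 to 10% for a true nadir of 50%, and 0 to 4% for 20%. The visit selected is not always Day 1.

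**Second dose.** For three assumed Day 29 to Day 56 profiles, each with a true nadir of 84%, the smallest reductions are 60%, 30% and 65%. The error is smaller here because suppression carries over from the first dose.

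**The case against.** The strongest reply is that a signed reading rescues the sentence. The SAP repeatedly writes percent reduction in the text where the matching figure is titled percent change. On a signed scale *lowest* is right, and *maximum reduction* can mean largest in magnitude. SAP 4.5.3 uses a maximum taken in absolute value for the laboratory shift tables. A reader might infer that no sign convention can reconcile the passage. The documents do not support that, because this convention would. What remains is that SAP 4.3.1 does not state it, and a derivation rule should not need it supplied.

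A reader might also count the figure titles as a further contradiction. They are better read as evidence of intent. With the individual-nadir definition and the word nadir itself, they make the intended rule recoverable, and most programmers would probably implement the greatest suppression. This part of the objection stands and is the main reason for a minor rating.

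A misapplied group nadir would also be visible. Percent change at every scheduled visit with 95% confidence intervals, mean percent change plotted over time, individual nadirs and the maximum reduction are all planned in SAP 4.3.1, and SAP 3.2 rules out formal testing.

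Two further inferences go beyond the text. One is that dose groups would be misordered or dose choice misled. That needs both a literal implementation that goes unnoticed and TTR profiles that the documents do not give. The other is that the definition governs the wild-type and mutant outputs. Figures 14.2.5.2 and 14.2.5.3 use the term, but they are LC-MS/MS outputs and SAP 4.3.1 is headed for the ELISA assay, so applying the rule to them is inference.

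**Conclusion.** Wrong as written, and minor. On the ordinary positive scale, which SAP 4.3.1 itself implies, the definition selects the least-suppressed visit instead of the most-suppressed one. The direction follows from algebra and rests on no assumption about the data. The size cannot be fixed from the documents: the illustrated gaps (for example 8% against 85%, or 0 to 16% against 80%) hold only for the assumed profiles and only if the sentence is programmed literally.

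The rule directly reaches the total-TTR percent-reduction summary and group-nadir plots for both dose intervals, and the group-nadir plots for vitamin A and RBP. The by-visit summaries, the individual nadirs and the safety analyses do not depend on it.

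**What to change.** In the defining phrase of SAP 4.3.1, change *lowest* to *greatest*, and add in brackets that this is equivalent to the lowest (most negative) mean percent change. Leave the windows as they are: Day 1 to the Day 28 premedication assessment and Day 29 to Day 56, or Day 1 to Day 21 and Day 22 to Day 42 for cohorts dosed every 3 weeks. Use this one definition for TTR, vitamin A and RBP.

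The cost is one phrase in the SAP. It needs no new data, tables or figures, and no output title has to change, because the figures are already on the percent-change scale.
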